Title: ACT for Post-Stroke Adjustment Via Telerehabilitation

Date Study Approved by REC: 23rd June 2025

Protocol Version 3 Date: 29th July 2025

Protocol Amendment Approval Date: 2nd September 2025

NCT Number: Pending

ACT for Post-Stroke Adjustment Via Telerehabilitation

Aims

The primary aim is to assess the preliminary efficacy of an adapted eight-week group of acceptance and commitment therapy (ACT), developed following Majumdar and Morris' 2019 study, that is delivered via telerehabilitation using idiographic methods.

The second aim is to explore the preliminary feasibility and acceptability of the intervention for adult stroke survivors.

Background

Stroke

With more than 1.3 million stroke survivors in the UK, stroke is considered one of the UK's main causes of disability (Stroke Association, 2017). The risk of stroke increases exponentially with age (Truelsen et al., 2006), but can have a detrimental impact on an individual's life regardless, affecting social interactions (Vickers, 2010), mood (Hilari, 2011) and activities of daily living (Hilari, 2011; Lazar & Boehme, 2017). Changes can be unexpected and difficulty adjusting could get in the way of rehabilitation (Mahmoud & Elaziz, 2016), affecting quality of life (QOL) (Bays, 2001; Jeong et al., 2012). Consequently, stroke survivors identify improvements to mental health services as an important research area (Weerasekara et al., 2021), and psychological intervention for wellbeing and adjustment is within the top 10 priorities for stroke rehabilitation (JLA, n.d.).

According to NICE (2023) Guidelines for psychological functioning in stroke rehabilitation, clinicians should assess changes to the way individuals adjust and cope, including monitoring of emotional functioning and behaviour. Specifically, Acceptance and commitment therapy (ACT) is recommended for those most at risk of anxiety or depression post-stroke (National Clinical Guideline for Stroke, 2023).

Acceptance and Commitment Therapy

ACT is a psychological intervention (Harris, 2019; McHugh, 2011) aiming to alter how individuals relate to distress following unexpected changes in circumstance, rather than change the distress itself (Hayes et al., 2006). ACT is therefore favoured for promoting wellbeing in adults living with long-term health conditions, including brain injury (Sander et al., 2021), chronic pain (Hughes et al., 2017), and multiple sclerosis (Han, 2021).

ACT incorporates the hexaflex model, referring to six core components of psychological flexibility (PF; Bond et al., 2015), where PF is the ability to act in line with our values (Doorley et al., 2020; Harris, 2019). The components include acceptance, contacting the present, values, committed action, self as context and defusion (Bond et al., 2015; Harris, 2019), which are grouped into a triflex of being present, opening up, and doing what matters (Harris, 2019).

In ACT, distress is considered normal due to the inevitability of adversity which prevents individuals from moving toward their goals and values (Harris, 2019). Cognitive therapies, however, argue a need to treat and therefore control distress (Hayes et al., 2006). This teaches clients to challenge their thoughts (Graham et al., 2015), undermining stroke survivors' understandably difficult circumstances (Gregg et al., 2007).

Consequently, ACT is preferred for addressing distress post-stroke because those with an acquired brain injury (ABI) must learn to accept their new difficulties/limitations and live with some uncertainty as part of moving forward with their life (Kangas & McDonald, 2011).

ACT Post-Stroke

The extent ACT reduces distress post-stroke is not yet known (Graham et al., 2015), possibly due to no consensus on the format/length of the intervention. However, many studies have started identifying the efficacy of ACT on wellbeing post-stroke and (more

generally, ABI populations) using numerous methods, including case studies, bibliotherapy, and single-case experimental designs (Gladwyn-Khan & Morris, 2023; Graham et al., 2015; Niu et al., 2022; Ooi & Steverson, 2023; Rauwenhoff et al., 2023; Sathananthan et al., 2022).

Considering current waitlists in healthcare and the cost of implementing interventions into the NHS, group-based psychological therapies could be more practical. In 2019, Majumdar and Morris conducted a four-week, face-to-face ACT group intervention that was adapted for stroke survivors. They found that ACT led to clinically significant improvements in depression and increased self-reported ratings of health status and hopefulness, compared to controls receiving treatment as usual (Majumdar & Morris, 2019).

Further research comparing ACT to other psychological interventions (such as cognitive behavioural therapy) would be beneficial in establishing its true effectiveness, providing a potential topic for systematic review. However, a significant problem with research thus far, and in particular Majumdar and Morris' (2019) study, is the focus on wellbeing, QOL and mood, rather than the constructs of ACT (Doorley et al., 2020). While important to monitor wellbeing with any psychological intervention and its pertinent links with acceptance (Lander, 2009; Simone et al., 2021; Townend et al., 2010), it remains unclear whether ACT achieves its primary aim in supporting stroke survivors to accept and adjust to their circumstances.

Consequently, qualitative research using a grounded theory approach with Majumdar and Morris' (2019) participants, found preliminary evidence that ACT helps those experiencing psychological distress when adjusting post-stroke (Large et al., 2019). Notably, this study also proposed modifications for the four-week intervention to improve accessibility which has not yet been assessed experimentally (Large et al., 2019). These modifications included extending the intervention from four to eight weeks and is currently being rolled out in a stroke healthcare setting in Wales NHS. As an initial monitoring of outcomes in a clinical

setting, the service uses the Short Warwick Edinburgh Mental Wellbeing Scale to monitor overall wellbeing and the UK Social Value Bank (HACT, 2017) to assess cost effectiveness of the intervention in regard to its impact on wellbeing and quality of life.

The literature therefore highlights a need for further research into the efficacy of ACT for post-stroke adjustment, including the empirical assessment of the modified ACT intervention from Majumdar and Morris' (2019) study.

Telerehabilitation

In addition to the benefits of group-based interventions in the NHS, the delivery of post-stroke healthcare via telerehabilitation (rehabilitation using technologies such as telephone, videoconferencing and web-based resources (Brennan et al., 2009; Signal et al., 2020)) is recommended in NICE (2023) Guidelines. Telerehabilitation improves accessibility of healthcare for those who cannot travel or access transport (Ostrowska et al., 2021). This is important given the risk of stroke increases exponentially with age (Truelsen et al., 2006) as older adults are more likely to have disabilities (Coleman, 2023) and/or live in rural or coastal areas far from healthcare services (Office for National Statistics, 2022).

To start assessing the efficacy of ACT via telerehabilitation, Ooi and Steverson (2023) conducted a case study, finding that six sessions improved psychological distress, depression and PF which was also maintained after six months. Given these findings, and a recent Cochrane review emphasising a need for more research into the efficacy of psychological therapy via telerehabilitation post-stroke (Laver et al., 2020), it is important to further explore the efficacy of ACT-based telerehabilitation for post-stroke adjustment.

Research Questions

Is group-based ACT delivered via telerehabilitation efficacious in managing post-stroke adjustment difficulties?

Is this intervention feasible and acceptable for adult stroke survivors?

Methods

Design

This is a single-case experimental design (SCED) using a small sample size and repeated collection of outcome measures (Krasny-Pacini & Evans, 2018).

In SCEDs, each participant serves as their own control (Tate & Perdices, 2019), but to improve validity and reliability, a multiple baseline design (MBD) will be adopted where participants are randomly allocated a baseline length before starting the intervention (Bouwmeester & Jongerling, 2020). This allows for longitudinal monitoring of stability in scores, improving confidence that changes observed are due to ACT and not other factors, evidencing “a potential treatment effect” (Slocum et al., 2022, p. 622).

According to Bouwmeester and Jongerling (2020), the MBD holds more power with groups of participants than single cases as outcomes in each phase are averaged. The revised “quality rating scale for [the] Risk of Bias in *N*-of-1 Trials” therefore argues a minimum of five datapoints at baseline (Tate et al., 2013, p. 619). This improves monitoring of the level, trend, and variability of data, which is important if attrition is high (Kratochwill et al., 2010). The baseline length will range from five to seven weeks.

Attrition is problematic when participant dropout causes less than five datapoints at baseline or occurs at a critical timepoint (e.g., during the intervention) (Kratochwill et al., 2010). Attrition at each stage will be reported in a flow chart, as per the Reporting Standards for Research in Psychology (APA, 2008).

The risk of attrition will be mitigated using a two-phase AB design, whereby A is the baseline (control), and B is the intervention (Levin et al., 2021). The longevity of change will be monitored three- and six-months post-intervention, reducing study demands compared to an ABA design where the second A acts as another control (Kazdin, 2021). Six-month follow-ups may occur after thesis submission for the purpose of publication if recruitment presents a challenge.

Participants

Nine adult stroke survivors will be recruited via NHS services (e.g., Early Supported Discharge Stroke Teams, IAPT services) and stroke charities. In SCEDs, six participants are recommended (Kratochwill et al., 2013), though nine will be recruited to account for attrition, with three being assigned to each baseline length (five, six, or seven weeks).

Inclusion

Adults (>18 years) will be included if they have:

- Suffered a stroke over three months ago.
- No other neurological illness.
- Not currently receiving any psychological intervention.
- No severe communication difficulties.
- No severe cognitive impairments.
- No current or historical suicidal ideation/self-harming behaviours.
- Not been diagnosed with major long-term health conditions in the last 12 months (except for stroke or trans-ischaemic attack; TIA).
- Access to a device with a camera, stable internet connection and private space.

Inclusion criteria ensure any changes are due to the intervention and not other factors such as spontaneous recovery from stroke which typically occurs within the first three months (Cassidy & Cramer, 2017; Zeiler, 2019); and other rehabilitative or psychological programmes. Criteria also ensures the monitoring of post-stroke adjustment rather than adjustment to other health conditions.

Exclusion

Participants will be excluded if they have:

- Had a TIA without the presence of a stroke.
- No current distress around adjusting to the consequences of stroke.

- Distress of a severity that it cannot be managed safely in a group therapy setting

Distress will be assessed using the Clinical Outcomes in Routine Evaluation – 10 (CORE-10) as it is considered valid and reliable in UK primary care populations (Barkham et al., 2013).

Measures

Outcome measures will be completed weekly, pre- and post-intervention or at three- and six-month follow-ups to reduce participant burden associated with frequent questionnaire completion. This is important as attrition is more likely amongst stroke survivors if studies are time-consuming (Weerasekara et al., 2021).

Less frequently collected measures were decided based on the secondary gains of ACT, the importance for between-study comparisons in assessing intervention efficacy and the second aim of feasibility and acceptability.

While some measures are not validated post-stroke, Bouwmeester and Jongerling (2020) suggest that the repeated collection of data in a SCED provides increased reliability in the test statistic.

CompACT-10

The Comprehensive assessment of Acceptance and Commitment Therapy Processes (CompACT) assesses PF (Francis et al., 2016) from the “three dyadic ACT processes”: openness to experience (OE), behavioural awareness (BA) and valued action (VA) (Golijani-Moghaddam et al., 2023, p. 60). The CompACT-10 (not attached due to copyright) has 10 items with acceptable to excellent internal consistency (Cronbach’s alpha, α , “total = 0.81, OE = 0.70, BA = 0.79, and VA = 0.75”), test-retest reliability (intraclass correlations, ICC, total = 0.83; OE = 0.86; BA = 0.76; VA = 0.89), convergent validity with the acceptance and action questionnaire-II ($r_s = -0.65$ and -0.70) and concurrent validity with

measures of wellbeing ($r_s = 0.66$ and 0.67) amongst UK-representative samples (Golijani-Moghaddam et al., 2023, p. 64).

Higher scores indicate greater PF (Golijani-Moghaddam et al., 2023) and will be completed weekly during baseline/intervention phases and repeated at follow-up.

Community Integrated Questionnaire (CIQ)

The CIQ has 15 items assessing participation in relation to three subscales: home/social integration and productivity (Wilier et al., 1994). Each item has a three-point scale and is totalled for an overall score, whereby higher scores indicate greater independence for activities such as managing finances, housework, employment/volunteering and socialising (Dalemans et al., 2010). Data will be collected pre/post-intervention and at follow-up.

The CIQ has high test-retest reliability ($ICC = 0.997$) amongst geriatric populations (Singh & Sharma, 2015) and good internal consistency ($\alpha = 0.71 - 0.84$) and test-retest reliability ($ICC = 0.91-0.97$) amongst adults with neurological conditions (Turcotte et al., 2019). The measure has also been extensively used in stroke research (Lee et al., 2015; Matos et al., 2020; Sathananthan et al., 2022).

Clinical Outcomes in Routine Evaluation-10 (CORE-10)

The CORE-10 is a 10-item questionnaire assessing psychological distress that is considered valid and reliable in UK primary care populations (Barkham et al., 2013). Each item is rated on a 5-point Likert scale from 'not at all' to 'most or all of the time' and provides a total clinical score where higher scores are indicative of more severe psychological distress (Barkham et al., 2013).

Amongst a post-acute stroke sample, the CORE-10 was considered to have high internal consistency ($\alpha = 0.80$) and test-retest reliability ($ICC = 0.81$) as well as acceptable

concurrent validity with measures of depression and anxiety ($r = 0.49 - 0.89$) (Steverson et al., 2024).

Aside from its validity and reliability, the CORE-10 was chosen due to its wide use in research and clinical settings, allowing for between-study comparisons and monitoring of wellbeing for early signposting (see 'Ethics: Risk Management'). This data will be collected pre/post-intervention and at follow-up.

Stroke-Specific Quality of Life (SS-QoL)

SS-QoL measures health-related QOL amongst stroke survivors (Vincent-Onabajo et al., 2016). The 12-item version refers to domains of self-care, mobility/upper extremity, language, vision, thinking, work/family/social roles, personality and mood/energy which are rated on a five-point scale to generate a mean total score and physical and psychosocial sub-scores (Post et al., 2011). The measure has good internal consistency ($\alpha = 0.77 - 0.89$) (Post et al., 2011) and is validated in a bi-ethnic stroke population (Kerber et al., 2013).

Higher mean scores indicate better QOL (Vincent-Onabajo et al., 2016). Data will be collected pre/post-intervention and at follow-up.

Short Warwick Mental Wellbeing Scale (SWEMWBS)

SWEMWBS is a seven-item questionnaire that monitors mental wellbeing (Stewart-Brown et al., 2009). Each positively phrased item is ranked on a Likert-scale of one (none of the time) to five (all of the time) and totalled to provide an overall score, whereby higher scores indicate better mental wellbeing (Stewart-Brown et al., 2009). The scale has been validated across clinical (Shah et al., 2021; Vaingankar et al., 2017) and non-clinical populations (Ng Fat et al., 2017), and is comparable to the 14-item version (Ng Fat et al., 2017). SWEMWBS is also considered responsive to change following therapeutic intervention at a group and individual level (Shah et al., 2018).

Beyond assessing mental wellbeing, the scale also assesses cost effectiveness of an intervention in regard to its impact on wellbeing and quality of life (HACT, 2017). Therefore, data will be collected pre/post-intervention and at follow-up.

Feasibility and Acceptability

Immediately after the intervention, participants will complete a questionnaire created for the purpose of this study to address the second aim on intervention acceptability. No gold standards for satisfaction scales currently exist, but they typically include satisfaction and staff skills (Miglietta et al., 2018).

Feasibility will be assessed using six criteria monitoring attrition, attendance and homework completion, as per previous research (Sathananthan et al., 2022).

Procedure

A poster will be circulated via NHS services and stroke charities, containing a link to an online survey (JISC, 2021). Here, participants can view the information sheet, consent form, and eligibility questionnaire. A consent to contact form and researcher contact details will be available should anyone prefer discussing the study before consenting to participate. To ensure accessibility to the study, the consent to contact form can be signed by the individual themselves or, if unable to sign (for example, due to physical impairment following stroke preventing ability to write, or due to healthcare appointments being held remotely), they can provide verbal consent to be contacted by the researcher to their clinician. The clinician can then sign the consent to contact form on their behalf.

Those meeting the inclusion criteria will attend a 30-minute video call to confirm eligibility, including ability to use videoconferencing platforms as per guidance for remote research (McCarthy et al., 2021). Guidance for accessing video calls will be provided.

Once a group is identified, participants will be randomly allocated to a baseline length (five, six or seven weeks) and provided a start date. Visual calendars will mark the dates of

each phase/task. Reminders and links to the questionnaire will also be sent weekly. During baseline and intervention phases, the CompACT-10 (Golijani-Moghaddam et al., 2023) will be completed weekly.

The intervention, delivered by the research team, lasts eight weeks. Each session is two hours, including breaks. Permission to access the protocol for the modifications to the intervention was granted (Large et al., 2019) and has been received. ACT training will be sought for the chief investigator prior to the study commencing.

Participants will have time at the end of each session for group reflections with reminders of where to access mental health support.

Immediately before and after the intervention phase and at three- and six-month follow-ups, participants will complete all questionnaires. At six-months, a 30-minute debrief will be offered.

As per the BPS Code of Human Research Ethics (BPS, 2021), all participants will receive a £10 gift card as reimbursement for their time.

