It is recommended that between-condition VA compares median rather than mean scores to minimise the influence of outliers (Lane & Gast, 2014). However, neither VA should be utilised in isolation (Lane & Gast, 2014) emphasising the importance of both for this project.

Reliable Change Index (RCI)

It is recommended that VA should be supported by statistical data analyses where possible (Bouwmeester & Jongerling, 2020; Morley & Adams, 1991). Therefore, RCI will be conducted to understand whether the change observed is significant and reliably exceeds what is expected from measurement error alone (Blampied, 2022; Jacobson & Truax, 1991).

Analyses will monitor changes between pre- and post-intervention scores and will be presented in a modified Brinley (scatter) plot (Blampied, 2022). Recommendations proposed by McAleavey (2024) will be considered.

References

- APA. (2008). Reporting standards for research in psychology: Why do we need them? What might they be? *The American Psychologist*, 63(9), 839.
- Association, S. (2017). *State of the Nation: Stroke Statistics*. <https://www.stroke.org.uk/stroke/statistics>
- Bays, C. L. (2001). Quality of life of stroke survivors: a research synthesis. *Journal of Neuroscience Nursing*, 33(6), 310-316.
- Blampied, N. M. (2022). Reliable change and the reliable change index: still useful after all these years? *The Cognitive Behaviour Therapist*, 15, e50. <https://doi.org/10.1017/S1754470X22000484>
- Bond, F. W., Lloyd, J., Flaxman, P. E., & Archer, R. (2015). Psychological flexibility and ACT at work. *The Wiley handbook of contextual behavioral science*, 459-482. <https://doi.org/10.1002/9781118489857.ch22>
- Bouwmeester, S., & Jongerling, J. (2020). Power of a randomization test in a single case multiple baseline AB design. *PloS one*, 15(2), e0228355. <https://doi.org/10.1371/journal.pone.0228355>
- BPS. (2021, 5th April 2021). *BPS Code of Human Research Ethics*. The British Psychological Society. <https://www.bps.org.uk/guideline/bps-code-human-research-ethics>

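### Baseline length is randomised, but no planned analysis uses the allocation or averages over participants, so the efficacy question has no safeguard against ordinary change over time with a known error rate

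*Combined protocol and SAP*

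**What the plan says.** The Design section adopts a multiple baseline AB design in which "participants are randomly allocated a baseline length before starting the intervention". It adds: "The baseline length will range from five to seven weeks". Under Participants, "In SCEDs, six participants are recommended", but "nine will be recruited to account for attrition", three per baseline length.

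The Design section supports this with a cited statement that "the MBD holds more power with groups of participants than single cases as outcomes in each phase are averaged". In the reference list, the paper cited for it is titled "Power of a randomization test in a single case multiple baseline AB design".

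The Analysis section names four methods: the percentage of non-overlapping data (PND), the percentage of data exceeding the median (PEM), within- and between-condition visual analysis, and the reliable change index (RCI) on pre- and post-intervention scores, shown in a modified Brinley plot. The RCI is introduced with the remark "It is recommended that VA should be supported by statistical data analyses where possible". No randomisation test, pooled model, significance level or group hypothesis is given. No outcome is labelled primary. The CompACT-10 is the only weekly measure, and Measures links the less frequent ones to the secondary gains of the therapy.

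**The concern.** Randomising baseline length makes it possible to ask whether scores change when therapy starts, rather than merely as weeks pass. The stated power rationale depends on combining participants. The planned analyses do neither: each compares a participant's later scores with that participant's earlier scores, and anyone improving steadily for another reason will tend to score well.

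The primary aim is preliminary efficacy, and the first research question asks whether the group therapy is efficacious. A favourable set of overlap indices would be read as an answer, although the chance of obtaining it without any effect is neither stated nor controlled.

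**Working it through.** **Inputs from the protocol.** Nine participants, 3:3:3 to 5, 6 or 7 baseline weeks (Design, Participants); weekly CompACT-10 and eight intervention weeks (Procedure), so 13 to 15 weekly scores each, with weeks 1-13 common to all; CompACT-10 total test-retest ICC 0.83 (Measures).

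**The plan's own figure.** There is no power, effect size or significance level to reproduce. Nine is the cited six plus an unstated attrition allowance: 6/(1 - 0.30) = 8.6, rounded up to 9, and 6/(1 - 1/3) = 9, so it fits dropout of about 30-33%.

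**What each planned analysis uses.**

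| Analysis | Data | Uses allocation? | Averages over participants? |
|---|---|---|---|
| PND, PEM | One person's weekly scores | No | No |
| Visual analysis | Level, trend and stability, within and between phases | No comparison across baseline lengths described | No |
| RCI | One pre and one post score | No | No; the plot displays participants together but tests nothing |

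**What the allocation could support.** Equally likely allocations and smallest one-sided p:
- Nine participants: 9!/(3!3!3!) = 362,880/216 = 1,680; 1/1,680 = 0.0006.
- Six participants (2:2:2): 6!/(2!2!2!) = 720/8 = 90; 1/90 = 0.011.
- A single case: 3 start points; 1/3 = 0.333, so 5% is unreachable.

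A 5% test is therefore available only if the allocation is analysed over the group.

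**Behaviour with no treatment effect.** Assumptions not in the documents: within-person weekly SD of 1, weekly autocorrelation between 0 and 0.3, a common linear drift, and 0.75 as the PEM cut-off. Share of nine-person trials in which most participants reach PEM of at least 0.75:

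| Drift (SD per week) | PEM at least 0.75 in most participants |
|---|---|
| 0 | about 2-6% |
| 0.05 | about 20-37% |
| 0.1 | about 54-79% |

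The lower end counts only intervention weeks up to week 13; the upper end counts all eight. The choice of autocorrelation moves these by several points. A one-sided 5% randomisation test on the mean intervention-minus-baseline difference over weeks 1-13 rejects in 4.8-5.5% of trials with nine participants and 4.5-5.3% with six, at drifts of 0 and 0.1 SD per week.

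**RCI.** Its threshold is 1.96 x sqrt(2 x (1 - 0.83)) = 1.14 SD of the score. It is set against measurement error, so drift is not addressed. If the nine are independent, the chance that at least one exceeds it in either direction by error alone is 1 - 0.95^9 = 37%.

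**Power of the randomisation test** (mean-difference statistic, same assumptions):

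| Immediate shift | Nine completers | Six completers |
|---|---|---|
| 1 SD | 52-56% | 35-38% |
| 1.5 SD | 82-85% | 62-64% |
| 2 SD | 96-97% | 83-84% |

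For gradual build-up to 1-2 SD with nine completers, power is only about 6-20%: 6-11% with the mean difference, with the upper end needing a statistic matched to sessions received. That gain depends on how the statistic is built; a simple per-person regression slope on sessions received does no better than the mean difference.

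**Two statistics.** Declaring success if either a level or a slope statistic reaches 5% gives a type I error of about 10%.

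**The case against.** The aim is stated as preliminary and idiographic, each participant is their own control, and no group test is promised. A reader might infer that the trial breaks a stated test or makes an unsupported power claim for its analyses. It does neither: no group hypothesis is stated, and the power sentence is a cited design rationale. This stands, and it makes the point one that should be fixed rather than one that invalidates the plan. What remains is the gap between the research question and design rationale on one side and the analyses on the other.

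A reader might also infer that nothing in the plan separates a therapy effect from ordinary change. That goes too far. Staggered baselines let stability be watched before therapy, visual analysis covers trend, and requiring a stroke more than three months ago limits spontaneous recovery. What is missing is a comparison across baseline lengths and a known error rate.

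The 54-79% result should not be quoted alone. It needs a drift of 0.1 SD per week and a cut-off the documents do not set, and it ignores the trend assessment planned beside PEM.

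The test also has limits. Power is low for gradual change, which is plausible for an eight-session therapy. Restricting to weeks 1-13 drops 3 x 1 + 3 x 2 = 9 of the 3 x (13 + 14 + 15) = 126 planned weekly scores, all from final sessions. And this is a group therapy: participants are randomised once a group is identified, and the text does not say whether therapy starts or only baseline starts are staggered.

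Some text after Procedure was not available to this review; the Analysis section itself reads as complete.

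**Conclusion.** The point holds as a gap that should be closed. The protocol randomises baseline length and appeals to power from averaging over participants, yet its four analyses use neither. Under assumed drift with no effect, a favourable PEM pattern ranges from about 2-6% of trials (no drift) to 54-79% (0.1 SD per week), while a test based on the allocation stays near 5%. The allocation counts and smallest p-values are exact. The simulated rates rest on assumed SD, autocorrelation, drift, effect shape and cut-off, because the documents give none of these. The test would supply validity, not assured power.

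**What to change.** 1. Label the weekly CompACT-10 total as the primary outcome.
2. Add, beside the individual analyses, one pre-specified randomisation test that permutes baseline lengths exactly as they were allocated, within group or recruitment wave if that is how it was done (for example 6^3 = 216 allocations for three waves of three).
3. Fix a single primary statistic, sidedness and level before data are seen, with a rule for missed weeks and dropouts. Any second statistic is supportive or multiplicity-adjusted.
4. State whether therapy start or only baseline start is staggered. If all start therapy on one date, acknowledge that a calendar event at session 1 cannot be separated from the treatment effect.
5. State the power limits above, and that a non-significant result is not evidence of no effect.
6. If the test is not adopted, remove or reword the power sentence in the Design section.

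Cost: a paragraph of analysis text and a short program, with no extra participants, visits or questionnaires. The price is a test that may well miss a gradual effect. Wider spacing of baseline lengths would raise power but lengthens the wait for distressed participants; it is a trade-off and not part of this fix.
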